Study Design	
Figure 1. Study Design
 
Each subject will use their own MiniMed™ 670G insulin system as usual. Each subject will be given 2 types of infusion sets to wear and change sets per label use (3 days for Quick-set™ and 7 days for EWIS). Each type of infusion set with the longest length (43" in) will be used for this study. 7-day reservoirs will be used with the Medtronic Extended and 3-day reservoirs will be used with the Quick-set™. The infusion set(s) or reservoir(s) can be replaced independent of each other for Medtronic Extended.
 
The subject will use either Medtronic Extended or Quick-set™ infusion set for consecutive 3 months. During the three-month period, either the right side or the left side of the abdomen will be designated for one or the other infusion set (defined randomly). For each type of infusion set, a coordinate rule for site rotation will be given to have the Set placed in a specified area (left or right side) of anterior abdominal wall (see appendix).
 
For each placement/wear, a daily log will be given to the subject to record time and location for the infusion set placement. Patients will be instructed to recognize areas of clinical apparent LH sites and refrain from inserting in these areas. At home, the subject will be expected to inspect their infusion site on a daily basis and if they observe signs of infection (i.e. erythema > 1 cm in diameter with warmth, pain, and/or induration) at the infusion site, they should call the investigational center. In addition to the study procedures, the subjects are to continue their standard routine care. In the end of each month, the subject should self-inspected by palpation for LH and record the findings on the daily log.
 
At each study visit, insulin pump and CONTOUR® NEXT LINK 2.4 study meter will be uploaded into CareLink™ Personal For Clinical Research. Also, all the infusion sites will be examined ultrasonically for LH.

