	
Enrolled subjects will have 5 investigational site visits.
 
Visit 1: Informed Consent and Screening.
 
Visit 2: Initial LH examination by ultrasound. Device training and Set 1 distribution (13 Medtronic Extended or 30 Quick-set™ infusion sets). A coordinate rule for site rotation will be given to have the Set 1 placed in a specified area (left side or right side) of anterior abdominal wall.
 
Visit 3: LH examination by ultrasound & Set 2 distribution (13 Medtronic Extended or 30 Quick-set™ infusion sets, different from Visit 1). A coordinate rule for site rotation will be given to have the Set 2 placed in opposite site of anterior abdominal wall used for Set 1.
 
Visit 4: End of study- 90 ± 7 days
 
Visit 5: 6-month examination
 
  
 Data Collection	VISIT 1*	VISIT 2*	VISIT 3*	VISIT 4* End of Study	Visit 5* Post-Study	
   
 Visit number	1	2	3	5	6	
 
 Informed consent	X					
 
 Enrollment screening	X					
 
 Demographics	X					
 
 Medical history	X					
 
 Local HbA1c	X			X	X	
 
 CareLink Clinical upload		X	X	X	X	
 
 Infusion set training		X	X			
 
 Diary collect and review			X	X	X	
 
 Collection of study sets			X	X		
 
 Ultrasound examination		X	X	X	X	
 
 Pain/comfort/Infusion set questionnaire				X	X	
 
 Adverse events and device deficiencies				X	X	
 
 Study deviations				X		
 
 *Unscheduled visit may be arranged upon patient observation of site reaction.	
  
	Data Collection	VISIT 1*	VISIT 2*	VISIT 3*	VISIT 4* End of Study	Visit 5* Post-Study	Visit number	1	2	3	5	6	Informed consent	X					Enrollment screening	X					Demographics	X					Medical history	X					Local HbA1c	X			X	X	CareLink Clinical upload		X	X	X	X	Infusion set training		X	X			Diary collect and review			X	X	X	Collection of study sets			X	X		Ultrasound examination		X	X	X	X	Pain/comfort/Infusion set questionnaire				X	X	Adverse events and device deficiencies				X	X	Study deviations				X		*Unscheduled visit may be arranged upon patient observation of site reaction.					

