Data Collection	VISIT 1*	VISIT 2*	VISIT 3*	VISIT 4* End of Study	Visit 5* Post-Study																																																																																												
Visit number	1	2	3	5	6																																																																																												
Informed consent	X																																																																																																
Enrollment screening	X																																																																																																
Demographics	X																																																																																																
Medical history	X																																																																																																
Local HbA1c	X			X	X																																																																																												
CareLink Clinical upload		X	X	X	X																																																																																												
Infusion set training		X	X																																																																																														
Diary collect and review			X	X	X																																																																																												
Collection of study sets			X	X																																																																																													
Ultrasound examination		X	X	X	X																																																																																												
Pain/comfort/Infusion set questionnaire				X	X																																																																																												
Adverse events and device deficiencies				X	X																																																																																												
Study deviations				X																																																																																													
*Unscheduled visit may be arranged upon patient observation of site reaction.																																																																																																	

Subject Stopping Rules
	
 1. Retracting of Patients consent 2. Unanticipated Adverse Device Effects (UADEs); 3. Diabetic Ketoacidosis (DKA); 4. Severe hypoglycemia events that result in subject requiring paramedic assistance, an Emergency Room (ER) visit or subjects who experience seizure, coma or death. 																																																																																																

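### The pain/comfort questionnaire is not scheduled at Visit 3, where Set 1 wear ends, so Set 1 is either rated from memory or not rated

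*Protocol*

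**What the plan says.** The Synopsis (Purpose/Objective) calls the study an infusion set crossover. Under Study Design, "The subject will use either Medtronic Extended or Quick-set™ infusion set for consecutive 3 months", and subjects "change sets per label use (3 days for Quick-set™ and 7 days for EWIS").

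The visit list gives out Set 1 at Visit 2. At Visit 3 it provides for "Set 2 distribution (13 Medtronic Extended or 30 Quick-set™ infusion sets, different from Visit 1"). Visit 4 is the end-of-study visit at 90 ± 7 days, with no stated starting point. Visit 5 is a six-month examination, headed as post-study in the data-collection table.

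That table has three rows that matter here:

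- "Collection of study sets" is marked at Visits 3 and 4.
- "Diary collect and review" is marked at Visits 3, 4 and 5.
- "Pain/comfort/Infusion set questionnaire" is marked at Visits 4 and 5, and is blank at Visit 3.

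Study Design describes the diary in two places: "a daily log will be given to the subject to record time and location for the infusion set placement", and at each month's end "the subject should self-inspected by palpation for LH and record the findings on the daily log". Neither mentions pain or comfort. Study Design also names questionnaires on pump routine, diabetes distress, treatment satisfaction and quality of life, but gives them no visit. The Exploratory Endpoints include pain and comfort questionnaires.

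**The concern.** In a crossover, a subjective rating of each treatment belongs at the end of the period in which it was used. Here the second period has such a rating and the first does not. The protocol does not say which set the Visit 4 and Visit 5 forms concern, which leaves two alternatives (they do not add up):

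- **Case A:** the Visit 4 form asks about both sets. Set 1 is then recalled after about three months on the other set, while Set 2 is rated fresh.
- **Case B:** the form asks only about the set in use. Set 1 then has no rating, and each subject contributes one set only.

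The timing of data collection is fixed by the visit schedule, so an analysis plan cannot repair this afterwards. The exploratory pain/comfort endpoint is at stake. Satisfaction is affected only if its instrument follows the same row of the table, which the protocol does not settle.

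**Working it through.** The protocol gives no figure to reproduce for this endpoint, and it states that no power assumptions are planned. The check is therefore of the timetable first and the consequences second.

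**1. Which visit ends Set 1?**
- Supply per period is 13 × 7 = 91 days (Extended) or 30 × 3 = 90 days (Quick-set), so one dispensing covers one three-month period.
- Set 1 is dispensed at Visit 2 and Set 2 at Visit 3. Used sets are collected at Visits 3 and 4 only.
- Set 1 therefore runs from Visit 2 to Visit 3, and Set 2 from Visit 3 to Visit 4. The end-of-wear visits are 3 and 4, and only Visit 4 has the questionnaire.

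**2. How old is a Set 1 rating taken at Visit 4?**
About 90 days by the supply. If the 90 ± 7 days is counted from Visit 3 (assumption), it is 90 − 7 = 83 to 90 + 7 = 97 days. At Visit 5 it is older still.

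**3. Case A: both sets rated at Visit 4, period-adjusted analysis.**
Let d be the true difference between sets A and B, and let rA and rB be the shifts when A or B is recalled.
- Order A then B: mean difference = d + rA.
- Order B then A: mean difference = d − rB.
- Average of the two sequence means = d + (rA − rB)/2.

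A shift common to both sets (rA = rB) gives zero bias. A gap rA − rB = D gives bias D/2. Both hold at any split that includes both orders. For an assumed D of 0.5 to 1 rating SD, the bias is 0.25 to 0.5 SD.

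Recall may also add independent noise of variance q·s², where s is the rating SD and ρ the within-subject correlation. The variance of a subject's difference rises from 2s²(1 − ρ) to 2s²(1 − ρ) + q·s², so the standard error is multiplied by √(1 + q/(2(1 − ρ))):

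| q (assumed) | ρ = 0 | ρ = 0.5 | ρ = 0.7 |
|---|---|---|---|
| 0.25 | 1.06 | 1.12 | 1.19 |
| 0.5 | 1.12 | 1.22 | 1.35 |
| 1 | 1.22 | 1.41 | 1.63 |

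**4. Case B: only the current set rated at Visit 4.**
With n1 and n2 subjects in the two orders:
- Between-subject variance = s²(1/n1 + 1/n2).
- Within-subject, period-adjusted variance with a rating at each end of wear = ¼(1/n1 + 1/n2) × 2s²(1 − ρ).
- Ratio = 2/(1 − ρ), whatever the split.

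| ρ (assumed) | Variance ratio | SE ratio |
|---|---|---|
| 0 | 2.0 | 1.4 |
| 0.3 | 2.9 | 1.7 |
| 0.5 | 4.0 | 2.0 |
| 0.7 | 6.7 | 2.6 |

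For example, with 16 completers split 8/8 and ρ = 0.5, the standard error is 0.50s instead of 0.25s.

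Both cases assume that both set orders are used. The visit list implies this, because either set may be the one given out first. With a single order, Case B would allow no comparison of the sets at all.

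**The case against.** The strongest reply is that the timetable is itself unclear. Neither the 90 ± 7 days at Visit 4 nor the six months at Visit 5 has a stated starting point, and the table's visit-number row runs 1, 2, 3, 5, 6. Counted from the start of wear, day 90 would end Set 1 and month 6 would end Set 2, and the questionnaire is marked at exactly those two visits. Diary collection, CareLink upload, HbA1c and adverse events at Visit 5 would fit that reading. It does not survive the rest of the document: Set 2 is already issued at Visit 3, sets are collected at Visits 3 and 4 but not at Visit 5, and Visit 4 is headed as the end of the study with Visit 5 after it. The ambiguity remains a reason for moderate confidence, and the timings should be reconciled.

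Second, the instrument is not shown. A preference form given once after both sets have been worn would be legitimate and could not be completed at Visit 3. That is true, but such a form still relies on recall of Set 1 and does not replace a rating at the end of its wear. The log template is not shown either, so the absence of pain entries is inferred from its description.

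Third, the protocol promises no formal set contrast for this exploratory item, and the values of D, q and ρ are assumed. Both statements are correct. They limit the weight of the point, but they do not remove the gap in a study set up to compare two sets in the same people.

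**Conclusion.** The concern holds and should be fixed. On the reading best supported by the protocol, 0 of about 16 completers rate both sets at the end of wear. With Visit 3 added, up to 16 of 16 could.

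The only size that comes from the document is the recall lag of about 90 days. The bias and standard-error ranges illustrate what follows under the stated assumptions, for whichever of the two cases applies. In Case A, a shared recall shift is harmless after period adjustment; a set-specific shift and added noise are not.

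Confidence is medium, because of the unseen instrument and the unanchored visit timing. The damage is confined to the exploratory pain/comfort endpoint, and possibly satisfaction. The primary lipohypertrophy endpoint is untouched.

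**What to change.** - Mark the questionnaire at Visit 3 as well as Visit 4. Have it completed at Visit 3 before Set 2 is handed out, and word each form to ask about the set just worn.
- Compare the sets within subject from these two ratings, with period in the model.
- State which set the Visit 5 form concerns.
- If the satisfaction instrument (for example the DTSQ) is meant to compare the sets, give it at the same two visits.
- In the same revision, state the starting points for the Visit 4 and Visit 5 timings and correct the visit-number row.

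The cost is one short questionnaire for each of up to 20 subjects at a visit they already attend, with no extra visit or test.

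### Adverse events, device deficiencies and study deviations are not scheduled at the crossover visit (Visit 3), so first-period events wait through the second period for their first scheduled collection

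*Protocol*

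**What the plan says.** The schedule of data collection in the Protocol synopsis has five visit columns. On this point it reads:

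- "Adverse events and device deficiencies": marked at Visits 4 and 5; blank at Visits 1, 2 and 3.
- "Study deviations": marked at Visit 4 only.
- "Diary collect and review": marked at Visits 3, 4 and 5.
- "Collection of study sets": marked at Visits 3 and 4.
- Ultrasound and CareLink upload: marked at Visits 2, 3, 4 and 5.

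According to the visit descriptions, Visit 2 issues the first set type, Visit 3 issues the other, and Visit 4 is the end of study at 90 ± 7 days. The starting point of that count is not given.

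Outside the scheduled visits there are two provisions. Subjects are to telephone the centre if they see signs of infection at the site (Study Design), and the schedule's footnote says "Unscheduled visit may be arranged upon patient observation of site reaction". On records kept by the subject, Study Design says "a daily log will be given to the subject to record time and location for the infusion set placement", and adds monthly self-palpation findings. The Subject Stopping Rules list unanticipated adverse device effects, diabetic ketoacidosis and certain severe hypoglycemia events.

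**The concern.** Visit 3 is the natural point to close the record of the first period. The subject is present, hands back used sets, has the diary reviewed and changes to the other set. Yet the two rows that would ask about harms, device faults and departures from the protocol are empty there. Followed literally, the plan first asks about first-period events after the subject has also worn the second set for about three months.

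Two things are at stake:

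- **Safety capture.** Three of the stopping rules depend on events that the schedule does not ask about until the end of study.
- **Even ascertainment.** The exploratory endpoints describe infusion-site pain, leakage, occlusion, accidental pull-out, adhesive problems, infection and erythema. Short-lived problems of this kind are easily forgotten or misdated. Where the summaries draw on the adverse event and deficiency record, events of the two periods would be recalled over different spans.

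**Working it through.** **Period length, reproduced from the supply.** The visit descriptions give 13 Extended sets or 30 Quick-sets per period; Study Design gives wear times of 7 and 3 days.

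- Extended: 13 × 7 = 91 days.
- Quick-set: 30 × 3 = 90 days.

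Both agree with the stated three months and with 90 ± 7 days.

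**Anchor for Visit 4 (assumption).** Put Visit 2 at day 0 and Visit 3 at day 90, and let Visit 4 fall V days after Visit 3, with V = 90 (83 to 97). If 90 ± 7 were counted from Visit 2, Visit 4 would fall on days 83 to 97, that is, within 7 days either side of Visit 3. That leaves no room for a second three-month period, so counting from Visit 3 is the more coherent reading. It is not stated, however. The examination at six months listed as Visit 5 does not settle it: counted from Visit 2, it would fall near day 180, where this reading already places Visit 4.

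**Wait from onset to first scheduled collection, as written.**

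- First-period event on day t (0 to 90): wait = 90 + V − t. With V = 90 the range is 90 to 180 days. With V from 83 to 97 it is 83 to 187 days.
- Second-period event: wait runs from 0 to V, so 0 to 90 days (at most 97).
- Visit 3 has no stated window. If the first period is also allowed to vary from 83 to 97 days, the first-period extremes become 83 and 97 + 97 = 194 days.

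**Mean wait, only if events are spread evenly over each period.**

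- First period: 45 + V = 135 days (128 to 142).
- Second period: V/2 = 45 days (41.5 to 48.5).
- Difference: 45 + V/2 = 90 days (86.5 to 93.5).

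**With Visit 3 marked.** First-period wait = 90 − t, so 0 to 90 days with mean 45, the same as the second period at V = 90.

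**What Visit 3 and the interval before it already cover.**

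| Type of event | Stated step at or before Visit 3 |
|---|---|
| Visible site reaction or infection | Skin assessment and ultrasound; telephone call for infection signs; optional unscheduled visit |
| Early set change | Placement times in the log; returned sets |
| Kinked or crimped cannula | Returned sets |
| Leakage, occlusion, pain | None stated as such; whether the diary or pump upload is read for these is not said |
| Diabetic ketoacidosis, severe hypoglycemia, non-site unanticipated device effects | None stated |

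The gap is therefore mainly in the last two rows.

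**The case against.** Much of the case on the other side stands.

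- **Attribution is mostly recoverable.** Each set type has its own side of the abdomen, and every placement is logged with time and location. A site event points to its set through the side, and any dated event through the crossover date. Only undated non-site events are hard to assign.
- **Set 1 and Set 2 are order labels.** Either device may come first. A reader might infer that one device's events are recalled over a longer span than the other's. The document does not support that: with mixed order, the longer wait falls on both devices. Study Design randomises the abdominal side and does not clearly say the same of set order, so a between-set bias can be neither shown nor sized.
- **The diary may hold more than is described.** The text names placement data and palpation findings but does not say that nothing else is recorded, and no form is shown. A reader might infer that reasons for set changes, leakage or pain are left out. That is silence, not a statement.
- **Data sources are not named.** The exploratory endpoints do not say that they are drawn from the adverse event row. The waits calculated above apply to that row and to the deviations row, not necessarily to every descriptive summary. Deviations such as early changes can already be seen in the log at Visit 3.
- **The stopping rules presuppose prompt notice.** They make sense only if the centre learns of such events when they happen. No route is written in the text at hand, although contact and consent pages were removed and might contain one.
- **The visit-number row runs 1, 2, 3, 5, 6.** The list of five visits suggests a numbering slip. If a contact between Visits 3 and 4 was lost, the wait would be shorter, but the Visit 3 cells would still be blank.

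This is also a pilot of about 16 completers with no power assumptions, and the affected summaries are descriptive. None of this puts a mark in the Visit 3 column, and none of the steps listed is described as adverse event, deficiency or deviation collection.

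**Conclusion.** The point holds as a gap in the schedule. Adverse events, device deficiencies and study deviations have no scheduled collection at the visit that closes the first period, and nothing in the text at hand makes collection continuous. This part rests on no assumption.

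The size is conditional. If Visit 4 is counted from Visit 3, the two periods' waits differ as calculated above, with the outer limits depending on the visit windows. The mean figures further require evenly spread events.

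The consequence is limited. The contrast is between periods, the primary lipohypertrophy endpoint is untouched, and site events are largely recoverable. What remains exposed is timely capture of non-site safety events and of transient device problems or pain. The correction is worth making because it concerns safety data, is specific and costs almost nothing.

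**What to change.** - Mark the adverse event and device deficiency row and the study deviation row at Visit 3 and at any unscheduled visit.
- Record, for every event, the onset date and the set worn at onset.
- Reconcile the schedule with the Subject Stopping Rules by stating how the listed events reach the centre between visits. The stopping criteria themselves stay as they are.

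While the table is open, state the visit from which Visit 4's 90 ± 7 days is counted and correct the visit-number row. The pain and comfort questionnaire row is also blank at Visit 3. It is outside this point but could be checked in the same edit.

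The cost is a few minutes at a visit that already takes place and already includes diary review and set collection, changes to two schedule rows, and two added fields on the event record. No extra visit or subject is needed. Under the same anchor, first-period events would then reach scheduled collection within 0 to 90 days, matching the second period.

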	
At each visit the clinical team will assess the skin in a systematic using the palpation method procedure and the US evaluation procedure (see appendix).
 
All participants will be asked to give demographic details and medical history. They will be asked to complete a series of questionnaires about their pump routine, diabetes distress, insulin treatment satisfaction and quality of life. All participants will have a baseline glycated hemoglobin (HbA1C) taken. The Total Daily Dose (TDD) will be calculated based on the CareLink™ data.

Sample Size and Investigational Center	
The study will be conducted at up to 1 investigational center. It is anticipated that approximately 16 subjects will complete the study.
 
Up to 20 subjects may be screened.
 
As this is an exploratory study - no power assumptions are planned.

Study Duration	The study is anticipated to last up to 12 months.
Inclusion Criteria	
Subjects will be considered for enrollment in the study if they meet all of the following criteria:
 
 1. Clinical diagnosis of type 1 diabetes and has been a pump user for at least 10 years 2. Using a MiniMed™ 670G or 640G Insulin pump with Guardian sensor 3. Age 18 to 80 years 4. Hemoglobin A1c level less than or equal to 10% 5. Not currently known to be pregnant, nor planning pregnancy during the study. 6. Willingness to follow the protocol and sign the informed consent 7. Use U100 Humalog (insulin lispro) or U100 NovoRapid/Novolog (insulin aspart)
Exclusion Criteria	
Subjects who meet any of the following criteria are not eligible for study participation and these exclusion criteria are study specific:
 
 1. Conditions that affect the skin evaluation, e.g. scleroderma or amyloidosis 2. A known medical condition that in the judgment of the investigator might interfere with the completion of the protocol. 3. Pregnant or lactating females 4. Subject has Glycosylated hemoglobin (HbA1c) > 10 % at time of screening.
LH Detection by Palpation and Ultrasound	LH identification by palpation and Ultrasound will follow literature method, as described in Gentile et al. SpringerPlus (2016) 5:563; A suitable palpation technique allows to identify skin lipohypertrophic lesions in insulin-treated people with diabetes

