Statistical Analysis for Endpoints and Hypothesis	
Primary Endpoint
 
The primary endpoint is the event rate of lipohypertrophy (LH).
 
The study will be evaluated and summarized, including but not limited to the following:
 
 • Self-assessed LH by palpation using a visual analogue scale (VAS) 1 to 10, coupled with clinical examination by a physician if possible • LH (appearance, location, mass, indices of vascularization and distribution) characterized by ultrasound. Standardized semiquantitative description will be used: variations in the thickness of the subcutaneous adipose tissue; single/multiple mass; size/dimension measurement; vascularisation index, flow index and vascularisation flow index; dense, fibrotic; localized, diffused, etc. • The relationship between the observed LH and infusion set type, TDD, glycemic control, HbA1C etc. • Satisfaction of infusion sets using validated questionnaire, e.g. the diabetes treatment satisfaction questionnaire (DTSQ) 
Statistical analysis may be performed for relationship determination.
 
Exploratory Endpoints
 
 • Descriptive of site reactions. Pain at the infusion site device related issues (leakage, occlusion in fluid path, etc.). • Descriptive of set failure cases: accidental pull out, adhesive tape issues, infection, erythema and/or induration. • Descriptive of catheter explants: • Gross examination for cannula kinking and crimping. • Pain and comfort questionnaires. • Samples of infusion set, insulin, and sensors will be stored for future analysis including microscopy and chemistry. 
Descriptive Endpoints
 
A number of Descriptive Comparisons of Interest will be made. They include, but are not limited to, the following
 
 • Continuous Glucose Monitoring (CGM) data, Time Above Range (TAR): Duration, and Area Under the Curve (AUC) when Sensor Glucose >180, >240, and >250 mg/dL • CGM data, Time Below Range (TBR): Duration, AUC when Sensor Glucose <50, <60, and <70 mg/dL • CGM data, Time in Range (TIR): Duration, AUC when Sensor Glucose > 70 e < 180 mg/dL • Glycemic variability: Standard Deviation (SD), Coefficient of Variation (CV), Mean Amplitude Of Glycemic Excursions (MAGE) • Cohort analysis by age • Cohort analysis by duration of diabetes
--	---

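### Time in range is written with open limits, so sensor readings of exactly 70 or 180 mg/dL fall in no range; if readings are whole numbers and are counted, time in range is slightly understated

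*Protocol*

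**What the plan says.** The synopsis row on statistical analysis for endpoints and hypothesis ends with a list of Descriptive Endpoints. Three consecutive items divide the sensor glucose scale:

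- Time above range: "Duration, and Area Under the Curve (AUC) when Sensor Glucose >180, >240, and >250 mg/dL".
- Time below range: "Duration, AUC when Sensor Glucose <50, <60, and <70 mg/dL".
- Time in range: "Duration, AUC when Sensor Glucose > 70 e < 180 mg/dL". The stray e is evidently the Italian word for and.

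No other part of the protocol restates these limits or says where a reading of exactly 70 or 180 mg/dL goes. The list is introduced with "A number of Descriptive Comparisons of Interest will be made", and the sample size row of the synopsis says "As this is an exploratory study - no power assumptions are planned".

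**The concern.** Time below, in and above range are normally read as a partition: each reading belongs to one of them, and together they account for all sensor time. As written they do not form one, because the two values at which neighbouring ranges should meet are excluded from both sides.

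The document itself shows where those values belong. A reading of 70 is not below range under the rule <70, and a reading of 180 is not above range under the rule >180. Only the middle range is left, and its rule shuts them out. Any loss therefore falls on time in range, while the other two ranges are as intended.

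The stake is small. The reported ranges may not quite add up, and a programmer must either follow the text literally or depart from it without saying so.

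**Working it through.** **Plan's own figure.** The protocol gives no figure for time in range, so there is none to reproduce.

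**Inputs from the protocol (Descriptive Endpoints).** Below: <70. In: >70 and <180. Above: >180 mg/dL.

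**Inputs assumed.** Readings in whole mg/dL; duration obtained by counting readings; glucose distributions as given below. None of these is in the protocol.

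**Step 1: coverage.** Each whole number from 40 to 400 mg/dL was tested against the three rules. Only 70 and 180 satisfy none of them.

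**Step 2: size under a normal model.** The share of readings at a whole value x is close to φ((x − mean)/SD)/SD, where φ is the standard normal density. The shortfall is the sum of this at 70 and 180. For mean 150 and SD 50:

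- at 70: φ(−1.6)/50 = 0.1109/50 = 0.22%
- at 180: φ(0.6)/50 = 0.3332/50 = 0.67%
- sum: 0.89%; × 1440 min = 12.8 min/day

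| Mean, SD (mg/dL) | Shortfall (points) |
|---|---|
| 140, 45 | 0.86 |
| 150, 50 | 0.89 |
| 155, 55 | 0.87 |
| 170, 60 | 0.82 |

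These shortfalls amount to 11.8 to 12.8 min/day.

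**Step 3: size under a lognormal model.** Let s² = ln(1 + CV²) and m = ln(mean) − s²/2, and let F be the resulting distribution function. The shortfall is [F(70.5) − F(69.5)] + [F(180.5) − F(179.5)]. For mean 155 and CV 36%, s² = ln(1.1296) = 0.1219 and m = 5.0434 − 0.0609 = 4.9825. The share at 70 is 0.179% and at 180 is 0.529%, together 0.71%. Time in range is 70.54% with open limits and 71.25% with closed limits.

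| Mean (mg/dL) | CV 30% | CV 36% | CV 42% |
|---|---|---|---|
| 140 | 0.62 | 0.74 | 0.84 |
| 155 | 0.68 | 0.71 | 0.76 |
| 170 | 0.74 | 0.70 | 0.71 |
| 185 | 0.77 | 0.69 | 0.67 |

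Entries are percentage points. They span 0.62 to 0.84, or 9.0 to 12.1 min/day.

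**Step 4: both models together.** The shortfall is 0.62 to 0.89 points, about 9 to 13 min/day. The three ranges total 100 − 0.89 = 99.11% to 100 − 0.62 = 99.38%.

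**Step 5: effect on the contrast between sets.** Take lognormal glucose with CV 36% and assumed means of 150 on one set and 160 on the other. The difference in time in range is 5.32 points with open limits and 5.33 with closed limits, a change of 0.01 point.

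**The case against.** The gap in the wording is plain; the harm is conditional. The protocol gives no sensor resolution. On a continuous scale, a reading of exactly 70 or 180 has probability zero and nothing is lost. Nor does it say how duration and AUC are computed. If the trace is treated as a curve between readings, a crossing of 70 or 180 takes no time, and only runs of identical boundary readings would drop out. Such computing detail is commonly left to a statistical analysis plan, which is not shown. All of this stands, and it is why the size is given only under stated assumptions.

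The practical effect is also slight. The same rule applies to both sets, the endpoint is descriptive, the study is exploratory, and the primary endpoint does not use these ranges. This stands too, and it sets the severity.

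A reader might infer more: that the rule is bound to give a wrong time in range, or that the results could not be set beside reports using closed limits. The document supports neither. The first needs whole-number readings and counting of readings. The second presumes outside figures that the protocol neither cites nor plans to compare with, and a gap of under one point would not make such figures incomparable.

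An inclusive sign might have been lost when the PDF was read. That cannot be excluded, but the same text keeps the sign in ≥ 16 subjects in the study design description, so the strict signs are probably as written.

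None of this removes the defect. The protocol does not leave the limits open; it fixes them, and fixes them with a gap.

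**Conclusion.** The point holds as a minor defect in a stated endpoint rule. It is certain from the text that 70 and 180 mg/dL are assigned to no range, and that by the protocol's own outer cut-offs neither value is below or above range.

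The numerical effect is conditional. With whole-mg/dL readings counted one by one, and glucose distributed as assumed above, time in range is low by about 0.6 to 0.9 percentage points. It would be wrong to read this as a bias in the comparison of infusion sets: the loss is nearly equal on both, and the contrast is practically unchanged. Severity: nice to fix.

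**What to change.** In the Descriptive Endpoints, define time in range as sensor glucose >=70 and <=180 mg/dL, with the stray e replaced by and. Leave <70 and >180 as they are. The three ranges are then exhaustive and mutually exclusive whatever the sensor resolution.

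The cost is two inequality signs and one word. Data collection, conduct and sample size do not change.
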